Clinical Investigation of Efficacy of Tauroursodeoxycholic Acid (TUDCA) to Enhance Pancreatic Beta Cell Survival In Type 1 Diabetes by Reducing Endoplasmic Reticulum Stress

National Clinical Trial Identifier: NCT02218619

Document Date: March 9, 2021

1. Study Purpose and Rationale

Hypothesis: An agent (TUDCA) that reduces ER stress will protect against the deterioration of beta-cell function in new-onset T1D.

Rationale: Abnormalities of ER stress responses contribute to the beta cell failure in early-onset T1D. Treatment of pre-diabetic NOD mice with TUDCA preserves beta cell mass and insulin secretion (see Background). In mice, TUDCA treatment also decreases lymphocytic infiltration of the islets and improves survival and morphology of beta- cells. Patients with newly- diagnosed T1D have a residual beta cell mass of 30-50% (c-peptide often >0.2 pmol/mL); beta cell destruction continues for at least 12-24 months after diagnosis until C-peptide is generally low or undetectable.

In this pilot study in human subjects with T1D, we will enroll 20 new-onset (within 100 days of diagnosis) subjects with measurable stimulated C-peptide (>0.2 pmol/mL).

2. Study Design and Statistical Procedures Also see Trial Flow Diagram

Visit -1 -Screening visit (+/- 3 days) Each participant must sign a consent form prior to screening. The screening visit consists of a medical history, physical exam, assessment of other medications that they may be taking and a review of their insulin usage and blood glucose values over the previous three days, blood tests including liver function tests, a urine test and a combination 2 hour Mixed Meal Tolerance Test (MMTT).

For females only: A sample of their urine will be utilized for a urine pregnancy test during the screening. Only the participant will be told the results of this test. If the test is positive, then they will not be able to participate. Females who are lactating are also ineligible for this study.

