i. Endpoints: The primary endpoints will be the area under the stimulated C-peptide curve of a 2- hour mixed meal tolerance test (MMTT) conducted at screening, and during the 12 months of drug treatment at 6 and 12 months and at 6 months after drug or placebo is stopped.

The study will also examine as secondary endpoints the effect of the experimental treatment on diabetes-specific autoantibodies and metabolic parameters. Interim metabolic assessments will consist of periodic review of glucose records and reports of hypoglycemia, insulin dose and HbA1c.

- ii. Trial Design: This single-center double-masked, Phase II placebo-controlled study will examine the efficacy of TUDCA to arrest beta cell hypofunction/destruction in 20 subjects with new- onset T1D (ages 18-45 years), randomized within 100 days of diagnosis). All subjects will receive standard intensive diabetes treatment with insulin and dietary management, consistent with American Diabetes Association Standards of Care. Diabetes management will be done by the primary diabetes care team at the Berrie Center. Subjects will be randomly assigned 1:1 to receive either daily TUDCA 1750 mg/day or placebo for 12 months. All subjects will be followed for until study end and will be offered option for re-contact in the informed consent so that longer-term study follow-up is a possibility. Enrollment is expected to occur over 18 months. The mean c-peptide responses to MMTT in the TUDCA treatment group will be compared to the placebo-treated group at 0, 6, 12 and 18 months. The study will also examine the effects of TUDCA treatment on other T1D- related metabolic and immunologic outcome measures.
- iii. Exploratory outcome: If a significant change in c-peptide responses are detected in both groups, we will compare the *in vivo* responses to ER stress relief to in-vitro responses to ER stress relief. In these subjects, we will compare the clinical response to an agent that reduce ER stress to the response of the iPS-derived beta cells, derived from the same subject, when treated with the same experimental agent to reduce ER stress.

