- iv. Treatment and Dose: Subjects will be treated with either TUDCA at a dose of 1750 mg/day or placebo for 12 months with an additional 6 months of follow-up. 1750 mg is the most commonly used dose used to treat biliary disease and was used in a recent study of human obesity and insulin resistance (39). In this 4 week study, an effects on ER stress was not observed on adipose cells; however we plan a longer treatment time period and hypothesize that since TUDCA undergoes extensive

hepatic metabolism, the exposure of pancreatic beta cells to drug at this dose may be sufficient to cause an effect on ER stress. In addition, in vitro studies will enable us to manipulate exposure of beta cells to a range of TUDCA concentrations, thus revealing extent of individual differences in sensitivity to the agent.

v. Duration: All subjects will be followed for 1 year of treatment and at least 6 months of follow-up.

VI DSMB: The progress of the study will be monitored by the DSMB which will review safety data and make recommendations regarding continuation, termination, or modification of the study. Based on an 18 month enrollment period and an additional study period of at least 6 months, the DSMB will formally review the safety data, enrollment, and clinical outcome data at least twice yearly.

Vii The number of subjects who discontinue study treatment will also be included in the reports prepared for the DSMB.

Statistical analysis: These studies are pilots in which we anticipate substantial interindividual differences in responses to the proposed *in vivo* intervention (TUDCA). We will compare the clinical endpoints between treated and control subjects using repeated measures ANOVA, treating (if indicated) age, gender and BMI as covariates. The endpoints of the in vitro studies will be analyzed for differences between individuals regardless of the experimental group to which they have been randomized. These analyses will inform us of the range of autonomous beta cell differences in response to ER stress, and to the mitigation conveyed by TUDCA. These data will then be related to clinical endpoints, probing for the ability of the *in vitro* studies to predict (correlate with) clinical course and response to TUDCA. We are experienced in all of the relevant analytic techniques and have the software on hand. If necessary, we have access to expert statistical consultations through the Columbia NIH CTSA.

3. Study Procedures MMTT and skin biopsy

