Aim: To assess the performance of canonical ER stress response pathways, including the ability of TUDCA to meliorate such stress *in vitro* in beta cells of the subjects of this study.

Rationale: As noted, there is growing recognition that ER stress plays an important role in beta cell responses to the immunologic and metabolic stresses that are the hallmarks of T1D. Pharmacological "relief" of ER stress is beneficial in rodent models of diabetes. Molecules that have these effects (e.g. TUDCA) are very well tolerated in children and adults to whom they have been administered for other indications.

Hypothesis: In patients with very recent onset of clinical T1D, TUDCA

administration will slow or prevent the advance of the disease.

Anticipated outcome: Individuals treated with TUDCA will show a trend toward preservation of beta cell mass and function as reflected in stimulated C-peptide in MMTT at 6 and 12 months of treatment compared to placebo; it is possible that if observed, this effect will still be present 6 months after cessation of treatment or later.

- 4. Name of investigational product: TUDCA
- i.Risks and Benefits: The known risks of drug treatment: In a summary of post-marketing data of 37 trials involving 1283 subjects treated with TUDCA up to 1750 mg/day for up to 1 year for severe liver disease, the most common side effect was diarrhea that occurred in .01% subjects. Less frequent adverse events were nausea, abdominal pain, pruritis, and headache.
- ii.Study drug and placebo are manufactured and supplied by Bruschettini (Genoa, Italy) and provided at no charge to study participants. The study drug is administered orally twice daily.

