 - iii. Population to be studied: New-onset T1D. We will recruit individuals between the ages of 18 and 45 with new- onset T1D (within 100 days of diagnosis). All patients will be in otherwise good health. Inclusion criteria will include: at least one diabetes- related autoantibody present (insulin autoantibody alone will not be sufficient in subjects treated with insulin for > 14 days) and a stimulated C-peptide levels > 0.2 pmol/ml measured during a mixed meal tolerance test (MMTT) conducted at least 21 days from diagnosis of diabetes and within one month (37 days) of randomization to either TUDCA or placebo. Pregnant women will be excluded. Participants of childbearing potential and/or their partners must agree to use acceptable methods of birth control beginning at the pre-study visit and throughout the study.

Examples of acceptable methods of birth control include abstinence, or 2 of the following: intrauterine device (IUD-with or without local hormone release), diaphragm, spermicides, cervical cap, contraceptive sponge, and /or condoms.

- iv. Drug handling/distribution/administration is conducted in accordance with the policies of the Research Pharmacy and Columbia University Medical Center
- 5. Study Instruments (e.g., Questionnaires, Interview Outlines, Focus Group Guides): N/A

6. Study Subjects

I. Subject Inclusion Criteria

- 1. Be between the ages of 18 and 45 years.
- 2. Be within 3 months (100 days) of diagnosis of T1D based on ADA criteria.
- 3. Must have at least one diabetes-related autoantibody present.
- 4. Must have stimulated C-peptide levels > 0.2 pmol/ml measured during an MMTT conducted at least 21 days from diagnosis of diabetes and within one month (37 days) of randomization.
- 5. If participant is female with reproductive potential, she must be willing to avoid pregnancy and have a negative pregnancy test during the 12 months of treatment and for an additional 3 months.
- 6. Must be willing to comply with intensive diabetes management.
- 7. Must be willing to undergo 3 mm skin biopsy at randomization.

II. Subject Exclusion Criteria

- 1. Be currently pregnant, lactating or anticipating getting pregnant.
- 2. Ongoing use of medications known to influence glucose tolerance.
- 3. Have serologic evidence of current or past HIV, hepatitis B, or C infection.

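### The plan names no tested term in its repeated measures ANOVA of C-peptide and does not adjust for screening C-peptide AUC, which costs precision or interpretability with 20 subjects

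*Combined protocol and SAP*

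**What the plan says.** All places are in the combined protocol and SAP.

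- **Section 2, Statistical analysis** is the only text on the clinical analysis: "We will compare the clinical endpoints between treated and control subjects using repeated measures ANOVA, treating (if indicated) age, gender and BMI as covariates". It does not say whether screening is a level of the repeated factor. It does not say whether group, group-by-time or a single-visit contrast is the test. It defines no change from screening.
- **Section 2.i, Endpoints**: "The primary endpoints will be the area under the stimulated C-peptide curve" from a 2-hour mixed meal tolerance test (MMTT), measured "at screening, and during the 12 months of drug treatment at 6 and 12 months and at 6 months after drug" or placebo ends. The screening value therefore counts as a primary measurement.
- **Section 2.ii, Trial Design**: the mean responses under TUDCA "will be compared to the placebo-treated group at 0, 6, 12 and 18 months".
- **Section 3, Anticipated outcome**: a trend toward "preservation of beta cell mass and function as reflected in stimulated C-peptide in MMTT at 6 and 12 months of treatment", relative to placebo.
- **Section 6.I, Inclusion Criteria**: "Must have stimulated C-peptide levels > 0.2 pmol/ml measured during an MMTT conducted at least 21 days from diagnosis of diabetes". This sets a floor for the starting level and no ceiling.
- **Size**: section 1 states "we will enroll 20 new-onset (within 100 days of diagnosis) subjects", and section 2.ii allocates them 1:1, so about 10 per arm.

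**The concern.** The anticipated benefit is preserved C-peptide during treatment. Statistically, that is a difference between arms after baseline, given the starting level. The plan names no contrast that estimates it, and each open reading answers a different question.

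1. **Group main effect over four visits.** Month 0 cannot carry a treatment effect, so averaging it in shrinks a sustained effect to three quarters of its size.
2. **Separate comparison at each visit.** There is no shrinkage, but baseline is not used, so a chance difference at screening carries into the estimate.
3. **Group-by-time.** This compares patterns of change, so baseline is used implicitly. The 3-df test yields no single treatment estimate, mixes two on-treatment visits with one off-treatment visit, and loses power if the effect peaks at one visit.

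With about 10 per arm, the choice among these can decide whether a real effect is seen and how it is described. Section 2.iii also makes an exploratory comparison conditional on a significant change in C-peptide, so a later step depends on a test that has not been defined.

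**Working it through.** The plan states no alpha, power, effect size or SD, so it has no figure to reproduce. The check compares the open readings under common assumptions.

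**From the documents:** 20 subjects, 1:1, so n = 10 per arm; four MMTTs (0, 6, 12, 18 months).

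**Assumed:** two-sided 0.05; equal SD at each visit, set to 1; equal correlation ρ between any two visits, taken as 0.5, 0.7 and 0.8; a true effect of 1 SD at every post-baseline visit unless stated; complete data.

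**Formulas.** The variance of the estimated difference is V × 2/n, with 2/n = 0.2. Power is from the noncentral t or F distribution, except for ANCOVA.

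- Four-visit main effect: V = (1+3ρ)/4 = 0.625 / 0.775 / 0.85; 18 df; expected estimate (0+1+1+1)/4 = 0.75 SD.
- Unadjusted month 12: V = 1; 18 df.
- Month 12 minus month 0: V = 2(1−ρ) = 1.0 / 0.6 / 0.4; pooled error, 54 df.
- Group-by-time: noncentrality (n/2) Σ(d−d̄)²/(1−ρ), where d is the effect at each visit. For d = (0,1,1,1) the sum is 0.75, giving 7.5 / 12.5 / 18.75; 3 and 54 df.
- Unadjusted post-baseline mean: V = (1+2ρ)/3 = 0.667 / 0.800 / 0.867; 18 df.
- Post-baseline mean minus screening: V = (4/3)(1−ρ) = 0.667 / 0.400 / 0.267; pooled error, 54 df.
- ANCOVA on screening AUC: simulated with an estimated slope, 17 df, 40,000 trials per setting. The large-sample V for the post-baseline mean is (1+2ρ)/3 − ρ² = 0.417 / 0.310 / 0.227.

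**Power, sustained 1 SD effect**

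| Analysis | ρ = 0.5 | ρ = 0.7 | ρ = 0.8 |
|---|---|---|---|
| Four-visit group main effect | 0.52 | 0.44 | 0.41 |
| Month 12, unadjusted | 0.56 | 0.56 | 0.56 |
| Month 12 minus month 0 | 0.59 | 0.81 | 0.93 |
| Group-by-time, 3 df | 0.59 | 0.83 | 0.95 |
| Month 12, ANCOVA | 0.66 | 0.82 | 0.93 |
| Post-baseline mean, unadjusted | 0.74 | 0.66 | 0.62 |
| Post-baseline mean minus screening | 0.77 | 0.93 | 0.99 |
| Post-baseline mean, ANCOVA | 0.89 | 0.96 | 0.99 |

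**Effect that peaks at month 12.** With d = (0, 0.5, 1, 0.5) the sum of squares is 0.5, the noncentrality is 5.0 / 8.33 / 12.5, and the 3-df test falls to 0.41 / 0.64 / 0.83. The single-visit month-12 analyses are unchanged.

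**Precision at month 12.** The mean 95% CI half-width is 0.93 SD unadjusted, 0.89 / 0.69 / 0.57 for change, and 0.83 / 0.68 / 0.57 for ANCOVA.

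**Correlation that decays with time** (adjacent visits 0.7 / 0.8 / 0.9). Month-12 power is 0.55 / 0.71 / 0.93 for change tested on its own 18-df error, and 0.65 / 0.76 / 0.94 for ANCOVA.

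**Chance imbalance.** The SD of the difference in mean screening AUC is √0.2 = 0.447. The probability that it exceeds 0.5 SD in either direction is 2[1−Φ(0.5/0.447)] = 0.26. A 0.5 SD imbalance moves the unadjusted month-12 estimate by 0.5ρ = 0.25 / 0.35 / 0.40 SD.

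**Type I error.** Simulated null rejection was 0.048 to 0.052 for every equal-correlation test and for the two decaying-correlation tests quoted.

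**The case against.** The strongest reply is that a repeated measures ANOVA with month 0 among its levels is naturally tested by group-by-time, which already uses baseline. On that reading the plan gives up little: for a sustained effect the 3-df test has 0.59/0.83/0.95 against 0.66/0.82/0.93 for month-12 ANCOVA, so it is 7 points worse at ρ = 0.5 and slightly better at 0.7 and 0.8. The worst case, the four-visit main effect, is stated nowhere. The trial also calls itself a pilot, expects only a trend and claims no power.

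Much of this stands. What is established is that screening AUC is not a covariate; under group-by-time it is still used. Against the change contrast, month-12 ANCOVA gains about 6 points at ρ = 0.5 and almost nothing at 0.7 to 0.8. The gain of 10 to 37 points applies only against an unadjusted month-12 comparison. Every magnitude is assumed. Equal SD across visits is doubtful in particular, since section 1 expects C-peptide to fall to low or undetectable levels, and the direction of the resulting error is unknown.

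The reply does not close the gap, because the plan does not choose group-by-time and the wording of section 2.ii points rather to comparisons visit by visit. Even if it were chosen, the 3-df test gives no single estimate of preservation, and it loses power when the effect is concentrated at one visit. Pilot status makes a usable estimate with its interval more important, and section 2.ii still describes a placebo-controlled Phase II study of efficacy.

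**Conclusion.** The concern holds. No tested term or contrast is named, screening C-peptide AUC is not an adjustment variable, and nothing elsewhere in the document supplies either. Under the stated assumptions, power for the same data and the same sustained 1 SD effect runs from 41% (four-visit main effect, ρ = 0.8) to 99% (post-baseline mean adjusted for screening AUC, ρ = 0.8), depending on a choice left open. The cost is largest under the main-effect and unadjusted readings. Under group-by-time it is small when correlation is high, apart from the missing single estimate.

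This is a loss of precision and interpretability. It is not a validity problem: type I error is preserved under these assumptions, and chance imbalance is not bias on average. The gap in the specification does not depend on the assumed figures; its size does. It should be fixed. Confidence is medium, because the documents give no SD, correlation or effect size.

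**What to change.** State the tested contrast in advance. Estimate the treatment effect from the 6-, 12- and 18-month visits with screening C-peptide AUC as a prespecified covariate, by mixed model or ANCOVA. An equivalent option is a longitudinal model that keeps month 0 as an outcome and constrains the two baseline means to be equal. Name one post-baseline contrast, for example month 12 at the end of treatment, report the adjusted difference with its 95% confidence interval, and treat the other visits as supporting. Say also whether age, gender and BMI stay in the model.

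The change is to analysis wording only; the screening MMTT is already required for entry. Baseline costs one parameter (month-12 ANCOVA: 20 − 3 = 17 error df instead of 18), or three if baseline-by-visit terms are included. The ANCOVA powers above already include the one-parameter cost. If age, gender and BMI are all kept as single terms, error df is 20 − 2 − 4 = 14 instead of 15, so screening AUC still costs one.

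### The primary C-peptide AUC analysis fixes no scale, AUC unit or baseline covariate, although values are expected to approach zero; prespecifying them is a cheap improvement

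*Combined protocol and SAP*

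**What the plan says.** Section 2.i makes the 2-hour mixed-meal C-peptide AUC the primary endpoint, measured at screening, at 6 and 12 months of treatment, and 6 months after treatment stops. For Months 0, 6, 12 and 18, Section 2.ii says "The mean c-peptide responses to MMTT in the TUDCA treatment group will be compared to the placebo-treated group". In the Statistical analysis paragraph the method is given as "We will compare the clinical endpoints between treated and control subjects using repeated measures ANOVA". Adjustment is described there only as "treating (if indicated) age, gender and BMI as covariates", so baseline C-peptide is not in the list.

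No section names a transformation, an AUC unit (total or time-averaged), or a value for results below the assay limit. The pmol/mL figure in Sections 1, 4.iii and 6 is the eligibility threshold for stimulated C-peptide, not a unit for the AUC.

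On the expected course, Section 1 says "beta cell destruction continues for at least 12-24 months after diagnosis until C-peptide is generally low or undetectable". On size, Section 2.ii says "Subjects will be randomly assigned 1:1 to receive either daily TUDCA 1750 mg/day or placebo for 12 months", which with 20 subjects is 10 per arm.

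**The concern.** An AUC cannot be negative, and here it is expected to move towards zero. If treatment works, placebo values may bunch near zero while treated values stay spread out. That fits poorly with the equal-variance, roughly normal errors of an ANOVA on untransformed values, and with 10 per arm one or two high values can dominate a mean.

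The plan leaves open how this will be handled. The scale, the unit, the value given to undetectable results and the use of baseline could all be settled after the data are seen, and each can move the result. Subjects are not replaced (Section 6.iii), so precision has to come from the analysis of data already planned.

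**Working it through.** **Timing.** The qualifying meal test is at least 21 days after diagnosis and randomisation is within 100 days of it. So randomisation falls about 0.7 to 3.3 months after diagnosis. Month 12 is then 12.7 to 15.3 months after diagnosis and Month 18 is 18.7 to 21.3. Both lie inside the 12-24 month span in Section 1.

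**Benchmark.** The plan gives no alpha, power, SD or effect size, so there is no figure to reproduce. Assume two-sided alpha 0.05 and a two-sample t-test on 18 df. The noncentrality is d x sqrt(10/2). For d = 1.32 it is 2.95 and power is 79.7%; for d = 0.8 power is 39.5%.

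**Simulations.** Every median, SD, decline and effect below is an assumption. AUC is time-averaged in pmol/mL unless stated.

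*Month-12 ANCOVA on baseline.* Proportional model: baseline log-normal, median 0.6, truncated above 0.2; Month 12 = baseline x exp(-0.6 + effect + error); the same log-SD, 0.4 to 0.8, for baseline and change.
- Effect of 1.3 log-SD: untransformed 47.0-66.7%, log(mean AUC + 1) 68.4-72.4%, a gain of about 6 to 21 points. The implied treatment ratio is exp(1.3 x 0.4) = 1.7 to exp(1.3 x 0.8) = 2.8.
- Fixed 1.5-fold effect, log-SD 0.4, 0.6, 0.8: 48% to 52%, 19% to 24%, 11% to 15%, a gain of 4 to 5 points.
- Additive decline floored at 0 (baseline mean 0.7, SD 0.25; effect 1.3 residual SD): 73.5-75.4% against 72.7-75.2%, a loss of about 1 point at most. On AUC in pmol/mL x min, power falls to 46-60%.
- No effect: rejection 3.8-5.3% on both scales.

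*Four-visit model* (0, 6, 12, 18 months; 20,000 trials per scenario). RM is the uncorrected group-by-time test.

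| Assumed scenario | Test | Untransformed | log(mean AUC + 1), pmol/mL | log(AUC + 1), pmol/mL x min |
|---|---|---|---|---|
| Log-normal, log-SD 0.6, slope SD 0.5, 2-fold | ANCOVA | 58.6% | 70.5% | not shown |
| Same | RM | 56.0% | 67.1% | not shown |
| Near-normal, additive, slope SD 0.1, +0.2 pmol/mL | ANCOVA | 91.2% | 90.7% | 72.6% |
| Same | RM | 87.7% | 87.1% | 53.4% |
| 15% undetectable by Month 12, 2-fold | ANCOVA | 55.2% | 51.5% | 21.9% |
| 30% undetectable by Month 12, 2-fold | ANCOVA | 32.0% | 28.4% | 9.6% |
| Effect only in the highest 30% by baseline | ANCOVA | 26.0% | 26.7% | 20.7% |

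Across the log-normal scenarios the gain on the pmol/mL scale was 2 to 16 points (ANCOVA) or 2 to 22 (RM). On pmol/mL x min the gain reached about 24 (ANCOVA), but the loss reached 87.7 - 53.4 = 34.3 points. The RM test rejected in about 8-11% of null trials on every scale, because sphericity fails when slopes vary. Its power figures are therefore flattered, and a log does not cure that.

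**Why the unit matters.** Take mean AUCs of 0.005, 0.35 and 0.7 pmol/mL.
- log(x + 1) gives 0.005, 0.300 and 0.531: steps of 0.295 and 0.231, nearly linear. Over 0.02 to 1 pmol/mL, log(x + 1) correlates 0.996 with x.
- In pmol/mL x min the values are 0.6, 42 and 84, and log(x + 1) gives 0.47, 3.76 and 4.44: steps of 3.29 and 0.68. Subjects near zero then dominate the error variance.

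**Baseline adjustment.** On untransformed data, Month-12 ANCOVA against an unadjusted Month-12 t-test gave 91.2% against 35.2% (near-normal row), 55.2% against 37.6% (15% undetectable) and 53.5% against 19.6% in one skewed scenario. In many scenarios this exceeds the effect of the transformation.

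**The case against.** The strongest case against is that a difference in means is a legitimate target for a pilot, that no document shows the data to be skewed, and that log(AUC + 1) taken literally on a 2-hour area could cost substantial power. All of that stands, and it is why the unit has to come with the transformation. It is also fair that repeated measures ANOVA with Month 0 as a level uses baseline through the group-by-time term, so the planned analysis need not be as weak as an unadjusted comparison. The plan does not say which term or contrast will be tested.

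Several stronger readings are tempting and not supported.
- A reader might infer that the plan commits to the untransformed scale. Comparing means by ANOVA suggests it, but no scale is stated.
- A reader might take "substantial interindividual differences in responses" as a statement that C-peptide levels are widely spread. The sentence concerns responses to TUDCA and bears on variance only indirectly.
- A reader might conclude that a log recovers power at almost no cost. There is no stated power to recover, the largest single-visit gain (21 points) needs a roughly 2.8-fold effect while Section 3 anticipates only a trend, and the cost depends on the unit.
- A reader might conclude that tests or intervals on the untransformed scale are invalid. Baseline-adjusted rejection under no effect was close to 5% on both scales, so the argument rests on power.
- A reader might think the +1 deals with undetectable values. It only avoids log(0) and sets no rule for results below the assay limit.

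**Conclusion.** The point holds as a prespecification gap with a cheap improvement. It is not an error that invalidates the analysis. The plan compares mean C-peptide AUC without fixing the scale, unit, undetectable-value rule or baseline covariate, in a setting where it expects values to approach zero.

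For time-averaged AUC in pmol/mL the balance favours the log scale modestly: about 2 to 22 points gained under right-skewed, proportional decline, against no gain or a loss of up to about 4 points under additive decline or 15-30% undetectable. For AUC in pmol/mL x min that balance does not hold, since losses of about 15 to 34 points are possible. Much of the gain over an unadjusted comparison comes from the baseline covariate. All sizes rest on assumed distributions and effects, so confidence in the magnitude is low. Confidence that the choices are unstated is high.

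**What to change.** Before unmasking, add to the Statistical analysis paragraph:

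1. The endpoint is time-averaged 2-hour AUC (AUC/120 min) in pmol/mL.
2. The primary analysis is of log(mean AUC + 1) at the post-baseline visits, with baseline log(mean AUC + 1) as a covariate.
3. One stated value is used for every result below the assay limit.
4. Arm estimates are back-transformed as exp(estimate) - 1 and reported with 95% CIs.
5. The untransformed, baseline-adjusted analysis is a sensitivity analysis.

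The cost is a few sentences; no new visits, samples or subjects are needed. The downside is that the treatment effect is estimated on a transformed scale rather than as a difference in means. A difference in log(mean AUC + 1) is a ratio of (AUC + 1), not of AUC, so readers will rely on the back-transformed arm estimates and the sensitivity analysis.

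### Correlating in vitro results with clinical endpoints cannot separate prediction of clinical course from prediction of response to TUDCA; the second needs an arm-by-index interaction

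*Combined protocol and SAP*

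**What the plan says.** Section 2.ii describes a parallel-group design: "Subjects will be randomly assigned 1:1 to receive either daily TUDCA 1750 mg/day or placebo for 12 months". The total is 20, so 10 per arm. The clinical endpoint in Section 2.i is the "area under the stimulated C-peptide curve of a 2- hour mixed meal tolerance test (MMTT"), measured at screening, 6 and 12 months, and 6 months after treatment stops.

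The Statistical analysis paragraph of Section 2 treats the in vitro work in two steps. First, the in vitro endpoints are "analyzed for differences between individuals regardless of the experimental group to which they have been randomized". Second, those data are related to the clinical endpoints, to probe the ability of the in vitro "studies to predict (correlate with) clinical course and response to TUDCA". So there are two targets, clinical course and response to TUDCA, and one named method, correlation.

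Section 2.iii adds a within-subject comparison: "we will compare the clinical response to an agent that reduce ER stress to the response of the iPS-derived beta cells" grown from the same person. It is to be done if C-peptide changes significantly in both groups.

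The only stated use of the placebo arm is the group comparison by repeated measures ANOVA, with age, gender and BMI as possible covariates. Nothing defines an individual's response to TUDCA, includes an index-by-arm term, or compares the association between arms.

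**The concern.** The two targets are different quantities. Predicting clinical course is prognosis: who loses C-peptide faster, whatever the treatment. Predicting response to TUDCA concerns the treatment effect: in whom the drug makes more difference. No subject is seen both on and off drug, so an individual's drug response is never observed. Only the C-peptide change is.

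Section 1 says that without an effective drug "beta cell destruction continues for at least 12-24 months after diagnosis until C-peptide is generally low or undetectable". Change in a TUDCA subject is therefore natural decline plus any drug effect. The trial's own rationale, that abnormal ER stress responses contribute to beta-cell failure, makes it plausible that a cell-based ER-stress index tracks decline, and the plan hopes that it predicts clinical course. If it does, it will also correlate with C-peptide change among TUDCA subjects when the drug does nothing. At stake is how an exploratory result is labelled: a prognostic marker could be described as a marker of drug benefit.

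**Working it through.** **No figure to reproduce.** The documents give no alpha, power, effect size, standard deviation or expected correlation. The expected effect is described only in words: "Individuals treated with TUDCA will show a trend toward preservation of beta cell mass and function".

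**Inputs from the documents.** 20 subjects, 1:1, so 10 per arm (Section 2.ii). Skin biopsy required of every subject at randomization (Section 6.I, criterion 7) and taken at Visit 2, when study drug is first supplied. The same MMTT schedule in both arms (Section 2.i).

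**Assumptions.** Two-sided alpha 0.05. Natural decline varies between subjects and has correlation rho with the in vitro index, shown from 0 to 0.7. Index and C-peptide change are bivariate normal, with change standardised to SD 1. The drug has no effect.

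**Step 1: what each association measures.** Let X be the index, D a subject's natural change in C-peptide, and B the drug effect in that subject.

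- Placebo arm: change = D, so cov(X, change) = cov(X, D).
- TUDCA arm: change = D + B, so cov(X, change) = cov(X, D) + cov(X, B).

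Randomisation makes cov(X, D) equal in the two arms in expectation, so the difference between arms is cov(X, B), the quantity meant by predicting response to TUDCA. A correlation in the TUDCA arm alone, or over all 20 subjects, leaves cov(X, D) in.

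**Step 2: size.** Simulated trials (100,000 per rho), percentage with p < 0.05. The tests are Pearson correlation in the TUDCA arm (8 df), Pearson correlation over all 20 subjects (18 df), and the difference in slopes between arms (16 df):

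| rho | TUDCA arm, n = 10 | All 20 subjects | Arm-by-index interaction |
|---|---|---|---|
| 0 | 5 | 5 | 5 |
| 0.1 | 6 | 7 | 5 |
| 0.2 | 8 | 13 | 5 |
| 0.3 | 13 | 25 | 5 |
| 0.4 | 21 | 43 | 5 |
| 0.5 | 32 | 64 | 5 |
| 0.6 | 49 | 83 | 5 |
| 0.7 | 68 | 96 | 5 |

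**Step 3: hand check at rho 0.5, n = 10.** The critical correlation is 2.306/√(8 + 2.306²) = 0.632, which is 0.745 on the Fisher z scale. The expected z is 0.549 + 0.5/(2 × 9) = 0.577, with standard error 1/√7 = 0.378. Then (0.745 − 0.577)/0.378 = 0.44, an upper tail of about 33%, in line with the simulated 32%.

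**Step 4: what the interaction can deliver.** With no prognostic effect, power to detect a true difference in slopes of 0.5, 1.0, 1.5 or 2.0 outcome residual SDs per index SD is 16%, 46%, 77% and 93%. With residual SD 1 and about 9 units of index sum of squares per arm, the 95% half-width is roughly 2.12 × √(1/9 + 1/9) = 1.0 on the same scale.

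**The case against.** Several objections have force.

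- **Under-specification.** The sentence about ignoring randomised group governs only the in vitro endpoints. The source cells are taken at the visit when drug is first supplied, so ignoring arm there is reasonable. The later sentence on clinical endpoints does not say whether arm is ignored. This stands: the plan leaves the step open and does not prescribe a wrong analysis. It still names no method other than correlation.
- **Which readout.** The plan has two: the cells' response to ER stress, and the mitigation that TUDCA gives in vitro. Sensitivity to ER stress may track natural decline, but nothing in the documents says that mitigation does. This is why rho must be shown from 0, where there is no inflation. Both readouts are nevertheless to be related to both targets.
- **The pooled column.** If the index truly tracks decline, a significant correlation over all 20 subjects is a correct finding about clinical course. It is wrong only if labelled response to TUDCA.
- **Status.** This is an exploratory analysis in a pilot with no decision rule attached. That excuses low power, but not answering a different question from the one named.

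A reader might infer more: that most of a subject's C-peptide change is natural decline, that the protocol says rates of decline differ between people, or that a prognostic marker would be reported as predicting drug response. The documents support none of these. They give no slope, spread or effect size. The between-person differences that they anticipate in vivo are in response to TUDCA. And the plan lists clinical course as a separate target, so a correct label is available.

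**Conclusion.** The point holds in a limited form. Correlation with clinical endpoints cannot tell a marker of decline from a marker of drug benefit, and no part of the plan uses the placebo arm to do so. With no drug effect, the correlation within the TUDCA arm is significant in 5% to 68% of trials as rho goes from 0 to 0.7, against about 5% for the interaction throughout. These rates rest on assumed variation in natural decline and an assumed rho. The argument itself needs only that decline and drug effect are mixed in a treated subject's change.

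Section 2.iii has the same weakness. A significant C-peptide change in both groups can arise from natural decline alone, so meeting that condition is no evidence of a response to TUDCA, and placebo subjects have no in vivo response to TUDCA to compare. The consequence is confined to the interpretation of an exploratory aim; the primary comparison of TUDCA with placebo is unaffected.

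**What to change.** In the Statistical analysis paragraph of Section 2, replace the single correlation with one model in all subjects: C-peptide change on in vitro index, arm, and arm-by-index. Report the slope in each arm. Describe an association shared by both arms as prognostic (clinical course). Reserve the statement that the index predicts response to TUDCA for the arm-by-index interaction, reported as an exploratory estimate with its confidence interval. Keeping both arms in one model avoids estimating prognosis from the 10 placebo subjects alone.

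Use the same definition in Section 2.iii, and say there that significant change in both groups does not by itself show drug response. Call a correlation within the TUDCA arm change on TUDCA, not response to TUDCA.

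The cost is a few sentences and no new data, since both arms already have the biopsy and the MMTTs. The downside is imprecision: with 10 per arm, and no replacement of subjects who withdraw, the interaction interval will be wide and any claim about prediction correspondingly weak.
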